## Research Plan: A. SPECIFIC AIMS:

Williams syndrome (WS) is a genetic disorder caused by a hemizygous microdeletion spanning 1.5 to 1.8 million base pairs containing 26 to 28 genes at chromosome 7q11.23. The prevalence of WS is estimated to be 1/7500 to 1/10,000. Multiple organ systems are affected by this microdeletion and there is a highly variable range and severity of cognitive and medical problems. Common medical comorbidities include cardiovascular disease, connective tissue abnormalities, growth abnormalities, and endocrine problems. In addition to the medical comorbidities associated with WS, many persons with WS experience high levels of psychiatric symptomatology including inattention, hyperactivity, and anxiety.

One of the areas receiving surprisingly little attention in WS is the diagnosis and treatment of anxiety. While children, adolescents, and adults WS frequently experience symptoms of anxiety, it has not yet been fully characterized. There are currently no published prospective studies on the pharmacologic treatment of anxiety in WS. There continues to be an urgent need for additional studies aimed at the treatment of anxiety in persons with WS.

The **long-term goal** of this research is to advance the evidence-base behind the pharmacological treatment of WS by studying medications that reduce maladaptive symptoms and improve the quality of life of the individual and his/her family members. The **primary objective** of this study is to conduct a preliminary prospective, open-label trial of buspirone for the treatment of anxiety associated with WS. The principal investigator (PI) and colleagues have completed a retrospective case series of buspirone, a serotonin (5-HT)1A receptor partial agonist and dopamine (D3 and D4) antagonist, for the treatment of generalized anxiety disorder in three individuals with WS and believe this to be a promising new treatment for the target symptom of anxiety.

The **central hypothesis** of this project is that buspirone will improve anxiety when administered to children, adolescents, and adults with WS. We also hypothesize that buspirone will be safe and well tolerated. This study will provide much needed pilot data regarding the effectiveness and tolerability of buspirone for these symptoms in WS and is a necessary first step prior to conducting a larger, more definitive randomized controlled trial.

We plan to provide preliminary evidence supporting the central hypothesis and accomplish the objectives of this study by pursuing the following specific aims:

- 1. Determine whether buspirone shows preliminary evidence of effectiveness, safety, and tolerability in children, adolescents, and adults with WS. This aim addresses our central hypothesis that buspirone will be effective and safe in the treatment of anxiety in persons with WS.
  - For preliminary evidence of effectiveness, we will require a significant decrease in mean PARS score from baseline and a ninety-five percent confidence interval for the effect size estimate consistent with a standardized effect size (difference in sixteen-week score from baseline divided by standard deviation at baseline) of one.
  - For preliminary evidence of safety, we will require no observation of serious or severe adverse effects possibly, probably, or definitely associated with buspirone.
  - For preliminary evidence of tolerability, we will require that the 95% confidence interval for dropout rate due to side effects of the drug be consistent with a rate of 20% or exclude values >=20%.
- 2. Determine which semi-structured interviews and existing anxiety rating scales would be most useful for characterizing participants and assessing anxiety treatment effects. A variety of outcome measures of anxiety will be used to better assess their applicability and feasibility in the WS population. The relative performance of the scales will be evaluated based on their sensitivity to change, their percent of item-level missing data, and any feedback on the appropriateness or ease of use of the scales from participants or study personnel.

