#### Sample Size Considerations:

Taking into account a likely placebo response, we consider a clinically meaningful decrease in mean PARS score 16 weeks after the start of buspirone to be equivalent to a standardized effect size (mean change/baseline standard deviation) of 1.0. Assuming a standardized effect size of 1.0, a correlation between baseline and week 16 measurements of 0.5, and a total loss to follow up of 30% (resulting in 14 participants providing complete data), a sample size of 20 participants provides greater than 90% power to detect a decrease in mean PARS score from baseline. In addition, for a standardized effect size of 0.2, a sample size of 20 provides nearly 80% power to rule out an effect size as large as 1.0.

For safety outcomes, if there is a serious or severe adverse event associated with buspirone treatment in the population that occurs with a frequency of 10% or more, we will have an 85% or greater chance of observing it in the study and concluding there are safety concerns with buspirone use in the population, assuming at least 90% (n=18) of participants remain in the study long enough to experience the event.

For tolerability, for discontinuation rates due to side effects of 50% or greater, a sample size of 20 provides 80% power to detect a difference from 20%, assuming no more than 10% dropout for unrelated reasons (n=18). All sample size calculations assume two-sided testing with alpha=0.05.

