#### **Statistical Analysis Plan:**

Demographic and clinical characteristics of the sample will be tabulated using means (SDs) for continuous characteristics and clinical scale scores treated as continuous and frequencies and percents for categorical and ordinal variables.

Change in PARS 5-item total score between baseline and week 16 will provide our primary preliminary estimate of efficacy. To estimate changes in PARS score and all other clinical outcomes but the CGI-I between baseline and week 16, we will use repeated measures linear regression models, as implemented in PROC MIXED in SAS and fit using REML estimation, with repeated measurements of clinical scores as outcomes and time, in categories, as the predictor. Our primary interest will be only in the difference between baseline and week 16 scores, but all observed scores will be included as outcomes, given that partially observed scores may be informative for estimation. We will obtain an estimate of 16-week change and corresponding 95% CI using a contrast of the week 16 and baseline model parameters. A contrast of the same parameters will provide a statistical test of the null hypothesis that there was no change in outcome between baseline and 16 weeks. For the CGI-I, we will estimate the percentage who respond to treatment and corresponding 95% CI using the proportion of participants with CGI-I scores <=2 at 16 weeks. For this calculation, participants who withdrew prior 16 weeks due to side effects will be included as non-responders, and participants who withdrew for other reasons will be excluded. Sensitivity to change will be compared between scales using standardized effect sizes, calculated using the estimated 16-week change in each outcome divided by the SD of the outcome at baseline. We will also tabulate and compare the percent of item-level missing data for each scale.

Frequency of all side effects and adverse events and corresponding 95% CIs will be tabulated. Tolerance and corresponding 95% CI will be estimated using the proportion of participants who did not withdraw from the study before 16 weeks due to reasons other than side effects or an adverse event who discontinue treatment due to side effects or an adverse event. We will also use the 16-week study retention rate and corresponding 95% CI, calculated as the proportion of the participants enrolling in the study who remain in the study for 16 weeks, as a measure of feasibility.

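### Aim 1's effectiveness rule has no clause for a confidence interval lying wholly above an effect size of one, so as written a better result than planned fails

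*Combined protocol and SAP*

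**What the plan says.** Section A (Specific Aims), Aim 1, sets two conditions for preliminary evidence of effectiveness. The first is significance: "we will require a significant decrease in mean PARS score from baseline". The second is "a ninety-five percent confidence interval for the effect size estimate consistent with a standardized effect size" of one, where the effect size is the week-16 change over the baseline SD ("difference in sixteen-week score from baseline divided by standard deviation at baseline) of one"). The text does not say at least one, and it has no alternative for an interval that excludes one on the favourable side.

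The tolerability condition in the same list is built differently. The interval for dropout due to side effects must "be consistent with a rate of 20% or exclude values >=20" per cent, so both an interval compatible with the limit and one wholly on the good side of it are accepted.

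Sample Size Considerations equates a standardized effect of 1.0 with "a clinically meaningful decrease in mean PARS score 16 weeks after the start of buspirone". It adds that, for a true effect of 0.2, "a sample size of 20 provides nearly 80% power to rule out an effect size as large as 1.0".

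The Statistical Analysis Plan does not restate the effectiveness rule. For the PARS it says "We will obtain an estimate of 16-week change and corresponding 95% CI", which concerns the raw change. The standardized effect appears only as a point value for comparing scales, "calculated using the estimated 16-week change in each outcome divided by the SD of the outcome at baseline". No interval method is given for it.

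**The concern.** An interval of, say, 1.1 to 2.3 excludes one. Read literally it is not consistent with an effect of one and fails the second condition, although it shows a larger benefit than the one planned for. The probability of success then rises and afterwards falls as the true effect grows, which a success criterion should not do.

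This rule decides whether Aim 1 reports preliminary evidence of effectiveness, and the trial is presented as the step before a larger randomized trial. If a large effect were observed, the team would have to report failure or reinterpret the rule after seeing the data.

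The low side of the second condition does useful work, because it screens out significant but weak effects. Only the upper side is missing.

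**Working it through.** **Inputs** (Sample Size Considerations): 20 enrolled, 14 with complete data, baseline to week-16 correlation r = 0.5, two-sided alpha 0.05. In baseline-SD units the SD of change is √(2(1 − r)) = √(2 × 0.5) = 1.0.

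**The plan's own figures.** Paired t-test, noncentral t, n = 14:
- True effect 1.0, testing for no change: power 93.2% (the plan says above 90%).
- True effect 0.2, ruling out 1.0 (a distance of 0.8): power 79.0% (the plan says nearly 80%).

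Both reproduce. The second supports reading the intended failure as an interval wholly below one.

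**Where the rule starts to reject good results.** The interval clears one when its lower limit exceeds one; t(0.975, 13) = 2.160.
- Baseline SD treated as known: the expected half-width is 2.160/√14 = 0.577, so the threshold is 1 + 0.577 = 1.577. It is 1.45 for r = 0.7 and 1.68 for r = 0.3.
- Delta-method interval, which carries the error in the baseline SD: for observed effect g the variance is 1/14 + g²/(2 × 19). Solving g − 2.160·√(1/14 + g²/38) = 1 gives g = 1.875. Check: √(0.0714 + 0.0925) = 0.405; 2.160 × 0.405 = 0.875; 1.875 − 0.875 = 1.000. The range is 1.76 to 1.97 for r = 0.7 to 0.3.

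**Probability of meeting the rule.** Simulation with normal data, 20 baseline values and 14 pairs, at least 200,000 draws per setting, r = 0.5. The plan does not name the interval, so three are shown.

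| Interval for the effect size | True effect 1.0 | 1.5 | 2.0 |
|---|---|---|---|
| As written, baseline SD known | 90% | 59% | 7% |
| As written, raw CI divided by sample baseline SD | 86% | 56% | 10% |
| As written, delta method | 91% | 83% | 34% |
| Upper side added, any of the three | 91–92% | 99.9% | 100% |

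At intermediate true effects of 1.25 and 1.75 the rule as written gives 85% and 26% (SD known) or 94% and 60% (delta).

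At the planned effect of 1.0 the loss is about 1 point (delta), 2.5 points (SD known) or 5 points (divided raw CI).

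**Sensitivity.**
- With SD known and n = 14, the pass rates as written at 1.0, 1.5 and 2.0 are about 80%, 68% and 17% for r = 0.3, and 95%, 39% and 0.6% for r = 0.7.
- Better retention makes the problem worse. With all 20 completing, the rule as written is met 44% of the time at 1.5 and 1% at 2.0 (SD known), and about 76% at 1.5 (delta).

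**Low side.** Adding the upper clause does not relax the screen for weak effects. At a true effect of 0 both wordings pass about 1.5% (SD known) or 1.7% (delta). With SD known, the second condition removes roughly 42%, 29% and 13% of significant results at true effects of 0, 0.2 and 0.5.

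**The case against.** The best defence is that the phrase is undefined and its purpose can be inferred. The sample size section treats 1.0 as the meaningful level and considers only failure from below, so a team following it would hardly call an interval wholly above one ineffective. But the tolerability rule uses the same construction and still spells out the favourable side. If being consistent with the limit already meant that or better, the second half of that rule would be redundant. The intended reading is clear; the written rule does not contain it.

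A second defence is that the harm is remote. No part of the plan predicts an effect above 1.0, the loss at 1.0 is small, and under the delta interval the rule as written still passes 83% at 1.5. This stands as a limit on the size of the problem. An observed value above 1.58 or 1.87 is not far-fetched, though. The trial is open-label, the plan itself expects a placebo response, and entry on PARS and CGI-S severity can narrow the baseline SD (the denominator) and bring regression to the mean.

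Third, this is an uncontrolled pilot of 20 people, the label has no regulatory or stopping consequence, and readers will see the estimate and interval. That is also fair, and it is why the point is a wording correction.

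Finally, the figures use complete-case paired t calculations, whereas the SAP fits a REML repeated-measures model to all observed scores, so they are approximate. The choice of interval method is a trade-off for the sponsor. That a method must be stated is not.

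**Conclusion.** The concern holds: the rule is wrong as written and should be corrected before data are seen. An interval wholly above one fails a criterion meant to show benefit, and no later section repairs it. The consequence is small at the planned effect and becomes large only when the true effect is well above it; the direction is the same under all three intervals examined. Sample size, the primary PARS change, its interval and its test are unaffected. The sizes rest on normal data, 14 completers, r = 0.5 (varied from 0.3 to 0.7) and an assumed interval method.

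A secondary gap also stands: the rule depends on an interval for the standardized effect that the SAP never defines, so the same data could pass or fail according to an unstated choice.

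**What to change.** Reword the second condition in Aim 1 along these lines, and repeat it in the Statistical Analysis Plan: *a 95% confidence interval for the standardized effect size that includes one or lies entirely above one (upper limit at least 1.0), with improvement counted as positive*. The direction needs stating because a week-16 minus baseline difference is negative when anxiety improves. Keep the significance condition and the low-side screen.

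Also state in the SAP how the effect-size interval is computed, preferably by a method that carries the error in the baseline SD, such as the delta method or a participant-level bootstrap. Dividing the raw interval by the sample baseline SD would cover only about 91% at an effect of 1.0 and 81% at 2.0, against 96–97% for the delta interval.

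The cost is one clause in Aim 1 and two sentences in the SAP, with no extra participants or data. The delta interval is wider than the divided raw interval by a factor of √(1 + 14g²/38): 17% at g = 1.0 and 57% at 2.0 (20% and 64% as simulated means). It also screens weak effects a little less, removing about 31% of significant results at a true effect of 0, against 42% with SD known. The sponsor can weigh that trade-off; the rewording does not depend on it.

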Confidence intervals for binomial proportions will be calculated using Wilson's method. Confidence intervals and statistical tests will be two-sided, with test-wise alpha=0.05.

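### The Aim 1 tolerability criterion treats failure to exclude a 20% side-effect dropout rate as evidence of tolerability, and is met with up to 6/18, 7/19 or 7/20 such dropouts

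*Combined protocol and SAP*

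**What the plan says.** Four parts of the combined protocol and SAP define the rule.

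- **A. Specific Aims, Aim 1.** Tolerability is supported if the 95% interval for "dropout rate due to side effects of the drug be consistent with a rate of 20% or exclude values >=20" percent.
- **Sample Size Considerations, tolerability paragraph.** For side-effect discontinuation rates of 50% or greater, "a sample size of 20 provides 80% power to detect a difference from 20" percent, "assuming no more than 10% dropout for unrelated reasons", which the plan equates with n = 18.
- **Statistical Analysis Plan, denominator.** The rate is taken among "the proportion of participants who did not withdraw from the study before 16 weeks due to reasons other than side effects" or an adverse event. Unrelated withdrawals therefore leave the denominator, and the evaluable number is 18 to 20.
- **Statistical Analysis Plan, interval.** "Confidence intervals for binomial proportions will be calculated using" Wilson's method, two-sided at the 5% level.

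Section A also says what the criterion serves. It states "We also hypothesize that buspirone will be safe and well tolerated", and says that the study "is a necessary first step prior to conducting a larger, more definitive randomized controlled trial".

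**The concern.** The second limb, an interval wholly below 20%, is a real demonstration. The first limb is not. An interval that contains 20% shows that the data are compatible with 20%, and usually with much higher rates too. Taken together, the two limbs are failed only when the lower limit lies above 20%. The burden of proof is thus reversed: tolerability is declared unless intolerability is shown, and with about 20 participants that takes a high dropout rate.

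At stake is the prespecified conclusion. Followed exactly, the plan would report preliminary evidence of tolerability when about a third of evaluable participants had stopped because of side effects. The sample size section gives power only at 50% or more, so it does not show how often the rule is met at true rates between 20% and 50%.

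**Working it through.** **Inputs.** Reference rate 20% (Aim 1). Wilson 95% limits, z = 1.96 (Statistical Analysis Plan). Evaluable n = 18, 19 or 20 (20 enrolled, at most 10% unrelated dropout). Alternative rate 50%, stated power 80% (Sample Size Considerations). The true rates of 5%, 25%, 30%, 35% and 40% used below are illustrative and not from the documents.

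**Formula.** With p = x/n, the Wilson limits are [p + z²/(2n) ± z·√(p(1−p)/n + z²/(4n²))] / (1 + z²/n).

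At n = 18:

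- x = 6: (0.4400 ± 0.2425)/1.2134 = 0.163 to 0.563. This contains 0.20, so the criterion is met.
- x = 7: (0.4956 ± 0.2492)/1.2134 = 0.203 to 0.614. This lies above 0.20, so the criterion is not met.

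**Step 1: the plan's own power figure.** The criterion is not met at x ≥ 7 of 18, x ≥ 8 of 19 and x ≥ 8 of 20. At a true rate of 50%, the binomial probabilities of those counts are 88.1%, 82.0% and 86.8%. Other methods at n = 18 give 83.6% (normal approximation with null variance), 77.9% (arcsine), 77.1% (continuity-corrected) and 76.0% (exact binomial). None of these gives exactly 80%, but 80% is a true floor under the interval that the plan specifies.

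**Step 2: the largest count that meets the criterion.**

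| n | Highest count met | Rate | 95% CI | Lower limit with one more |
|---|---|---|---|---|
| 18 | 6 | 33.3% | 16.3% to 56.3% | 20.3% |
| 19 | 7 | 36.8% | about 19% to 59% | 23.1% |
| 20 | 7 | 35.0% | 18.1% to 56.7% | 21.9% |

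All three intervals include 50%.

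**Step 3: when the stronger limb is met.** The upper limit with zero events is 17.6%, 16.8% and 16.1% at n = 18, 19 and 20. With one event it is 25.8%, 24.6% and 23.6%. Only zero side-effect dropouts exclude 20%, so any pass with one or more such dropouts rests on the first limb alone.

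**Step 4: probability of meeting the criterion**, P(X ≤ highest count met):

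| True rate | n = 18 | n = 19 | n = 20 |
|---|---|---|---|
| 25% | 86% | 92% | 90% |
| 30% | 72% | 82% | 77% |
| 35% | 55% | 67% | 60% |
| 40% | 37% | 49% | 42% |
| 50% | 12% | 18% | 13% |

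**Step 5: reach of the stronger conclusion.** At a true 5% rate, the probability of zero events is 0.95^n, which is 40%, 38% and 36% at n = 18, 19 and 20.

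**The case against.** The best defence is that the rule is openly stated and matches its sample size paragraph. Both describe a test for departure from 20%, which works as a screen for gross intolerability in a small uncontrolled pilot. The evidence is called preliminary. The interval will be reported, so a reader shown 6/18 with limits of 16% and 56% can see the uncertainty. All adverse events and 16-week retention are also tabulated with intervals, and Aim 1 has a separate, strict safety criterion. Requiring exclusion of 20% would rarely succeed with 20 participants even if the drug were well tolerated (Step 5).

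Most of this stands, and it limits the harm. It does not repair the rule, because none of it stops the tolerability conclusion from being drawn at about 35% side-effect dropout. The safety criterion covers only serious or severe effects, so dropout for mild or moderate ones would not trigger it.

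A reader might infer three stronger points that the documents do not support.

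- *That the power statement or sample size is wrong.* Step 1 shows that 80% is conservative under Wilson.
- *That the rule cannot separate good from bad tolerability at the plan's own assumed attrition.* The figure of "a total loss to follow up of 30" percent belongs to the efficacy calculation. The tolerability paragraph makes its own assumption of at most 10% unrelated dropout, so evaluable numbers below 18 fall outside it.
- *That 30% is a rate the plan regards as unacceptable.* The plan sets no such limit; 20% is only its reference rate.

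**Conclusion.** The concern holds as a fault in the decision rule, not in the arithmetic or the design. The tolerability conclusion would be drawn at any result up to 6/18, 7/19 or 7/20. A true rate of 30% would earn it 72% to 82% of the time, and a true rate of 40% would earn it 37% to 49% of the time.

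These figures rest on the Wilson interval, on reading consistency with 20% as the interval containing 20%, and on 18 to 20 evaluable participants. The two-limb wording and the power statement both support that reading. The 30% and 40% rates are illustrations.

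It would go too far to say that the result decides whether a randomized trial goes ahead. The plan calls the pilot a necessary first step, but no section makes this verdict a go/no-go gate. The consequence is an overstated Aim 1 conclusion, which should be corrected before the results are reported.

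**What to change.** Two additions are needed.

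(a) In Specific Aim 1, after the tolerability criterion: *Meeting the criterion through consistency with 20% means only that a 20% rate was not excluded. A side-effect dropout rate below 20% will be concluded only if the upper 95% limit is below 20%. The upper limit will be given with the tolerability conclusion.*

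(b) In Sample Size Considerations, after the tolerability power statement: *Under the Wilson interval the criterion is not met at 7 or more side-effect discontinuations of 18, 8 or more of 19, or 8 or more of 20; at an illustrative true rate of 30% it would still be met with probability 72%, 82% and 77%.*

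The cost is wording only. Sample size, data collection and analysis stay as they are, and the 80% power statement can remain. The price is a more modest claim: the stronger conclusion needs zero side-effect dropouts, which even at a true 5% rate would occur only 36% to 40% of the time.
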